**Lanifibranor tablets taken:**

The total number of lanifibranor tablets taken corresponds to the sum of the number of lanifibranor tablets taken in each bottle at each visit.

If the date of last intake reported on the EOT form is  $\leq$  date of post-treatment biopsy then tables taken is equal to the number of tables taken up to Visit 3 (see definition above in section compliance at visit(i)).

If the date of last intake reported on the EOT form is  $>$  date of post-treatment biopsy then tables taken is equal to the number of tables taken up to Visit 3 (see definition above in section compliance at visit(i)) minus  $3 \times (\text{Date of last intake reported on the EOT form} - \text{date of post-treatment biopsy})$ .

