#### 4.3.2 Treatments Administered

This double blinded placebo controlled study involves a therapeutic dose of 800 mg lanifibranor (qd) and 1200 mg lanifibranor (qd).

[figure not shown]
The lanifibranor tablets and PTM are packaged into High-density polyethylene (HDPE) bottles of 100 ml (38 tablets for a treatment period of one month, plus a use margin of 1 week) with proper closures fitted with a silicagel cartridge. Three bottles each (either active or placebo) and labelled A, B and C with a colored circle sticker are assembled in a carton to compose monthly Kits as detailed below:

- Placebo Kit: Morning (P+P+P)
- 800 mg Kit: Morning (P+A+A)

- 1200 mg Kit: Morning (A+A+A)

Where P denotes the placebo tablet and A denotes the active tablet (400 mg).

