**Lanifibranor tablets to be received up to the time of biopsy at week 24:**

The total number of lanifibranor tablets to be received is equal to:

- $((\text{Date of biopsy at week 24} - \text{Study first treatment intake date} + 1) \times 3)$  for patients receiving lanifibranor at the dose of 1200 mg
- $((\text{Date of biopsy at week 24} - \text{Study first treatment intake date} + 1) \times 2)$  for patients receiving lanifibranor at the dose of 800 mg

4.5.6.2 *Adverse Event data*

- **Treatment Emergent Adverse Event**

A Treatment Emergent Adverse Event (TEAE) corresponds to an Adverse Event (AE) that occurred on or after first dose of treatment up to 28 days post-last dose.

- **Treatment Emergent Adverse Events related to study treatment**

TEAE related to treatment is defined as a TEAE having a relationship to treatment equals to “Possibly related”, “Probably related” or with a missing relationship to study treatment.

Relationship equals to “Unlikely Related” will be considered as not related.

- **Non-Treatment Emergent Adverse Events (non-TEAEs)**

Non-TEAEs are AEs that occurred prior to treatment start.

- **Post-Treatment Adverse Events (PTAEs)**

PTAEs are AEs that occurred more than 28 days after end of treatment.

- **Serious Adverse Events**

By definition, a serious AE (SAE) is an AE that, at any time, fulfils one or more of the following criteria:

- results in death,
- is life threatening (the subject was at immediate risk of death at the time of the event; it does NOT refer to an event which hypothetically might have caused death if it were more severe),
- requires in-subject hospitalisation or prolongation of existing hospitalisation,
- results in persistent or significant disability/incapacity (substantial disruption of a person's ability to carry out normal life functions),
- is a congenital anomaly/birth defect,
- is any important medical event that may not be immediately life threatening or result in death or hospitalisation but, based upon appropriate medical judgment, may endanger the subject or may require intervention.

The seriousness of the event will be directly assessed by the investigator (specific variable within the AE database); therefore no derivation is needed.

- **Onset day**

Onset day is defined as the time between the first treatment intake date and AE onset date: (AE onset date – date of first intake + 1).

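### SAP 4.5.6.1: in the active-bottle compliance measure, the 800 mg numerator does not match its two-tablets-per-day denominator

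*SAP*

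**What the plan says.** The measure is the last item of SAP 4.5.6.1 (Treatment data): overall compliance at the time of the week-24 biopsy, based on lanifibranor bottles.

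- **Numerator, opening sentence:** "The total number of lanifibranor tablets taken corresponds to the sum of the number of lanifibranor tablets taken in each bottle at each visit". This is a count of active tablets.
- **Numerator, last intake on or before the biopsy:** the tablets taken up to Visit 3, by cross-reference to the per-visit compliance definition. Nothing is subtracted.
- **Numerator, last intake after the biopsy:** the rule reads "then tables taken is equal to the number of tables taken up to Visit 3 (see definition above in section compliance at visit(i)) minus"; what is then removed is 3 tablets for each day from biopsy to last intake. There is no split by dose. (The word for tablets is misspelt in the SAP.)
- **Denominator:** days from first intake to biopsy, inclusive, multiplied by 3 for 1200 mg and by 2 "for patients receiving lanifibranor at the dose of 800 mg".

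The per-visit definition referred to sums tablets over all bottles, without separating active from placebo.

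Protocol 4.3.2 gives the kit contents: "800 mg Kit: Morning (P+A+A") and "1200 mg Kit: Morning (A+A+A"), where P is a placebo tablet and A an active 400 mg tablet. SAP 5.3.1 lists the measure among the exposure variables to be summarised descriptively by treatment group in the safety set, next to the all-bottle version.

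**The concern.** An 800 mg patient who follows the instructions takes two active tablets a day. The denominator recognises this; the post-biopsy subtraction does not. The same three-per-day term stands in the all-bottle measure immediately above, where the denominator is also three per day and the term is right. It appears to have been carried down without the dose split that the denominator received.

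The cross-reference is a second, separate problem. The opening sentence calls for active tablets, but the branch rules point to a count that includes the placebo bottle. Two programmers could therefore obtain quite different values for the same 800 mg patient. That matters if this variable falls under the independent double programming in SAP 4.1.3.

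At stake is the accuracy of one reported row. Its purpose is to show exposure to active drug when the primary-endpoint biopsy was taken. As written, it can show a gap between the two doses that is purely arithmetic.

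**Working it through.** The SAP states no compliance value to reproduce, so the check applies its formula to a patient who misses no tablets.

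**Inputs**
- a = active tablets per day: 2 for 800 mg, 3 for 1200 mg (Protocol 4.3.2; SAP denominators).
- D = days from first intake to biopsy, inclusive. Planned treatment is 24 weeks (Protocol 4.3.3), or 24 × 7 = 168 days. A biopsy 168 days after first intake gives D = 168 + 1 = 169.
- k = days from biopsy to last intake. The documents do not give k; 0 to 14 days is assumed.

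**Reading (a): active bottles only**

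SAP compliance = [a(D + k) − 3k] / (aD).

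- 1200 mg: [3(D + k) − 3k] / (3D) = 100% for every k.
- 800 mg: [2(D + k) − 3k] / (2D) = 100% − k/(2D).

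With D = 169 the 800 mg denominator is 2 × 169 = 338:

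| k (assumed) | Active tablets taken | Subtracted by SAP | Numerator | 800 mg compliance | Shortfall (points) |
|---|---|---|---|---|---|
| 0 | 338 | 0 | 338 | 100.0% | 0 |
| 1 | 340 | 3 | 337 | 99.7% | 0.3 |
| 3 | 344 | 9 | 335 | 99.1% | 0.9 |
| 7 | 352 | 21 | 331 | 97.9% | 2.1 |
| 14 | 366 | 42 | 324 | 95.9% | 4.1 |

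The result depends little on D. From D = 162 to D = 183 the shortfall runs from 2.2 to 1.9 points at k = 7 and from 4.3 to 3.8 points at k = 14. To bring a fully compliant patient below 95% takes 0.05 × 338 = 16.9, so about 17 post-biopsy days.

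**Reading (b): all three bottles, following the cross-reference**

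800 mg: [3(D + k) − 3k] / (2D) = 3D/(2D) = 150%, whatever k is. At D = 169 and k = 7: (528 − 21)/338 = 507/338 = 150%. With the last intake on the biopsy day nothing is subtracted and the value is again 507/338 = 150%. Here the subtraction agrees with the count; it is the count that does not fit the denominator. For 1200 mg all three bottles are active, so the result is 507/507 = 100%.

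**After the correction**

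Counting active bottles only and subtracting a × k gives [a(D + k) − ak] / (aD) = 100% in both dose groups for every D and k. At k = 7 for 800 mg: (352 − 14)/338 = 100%.

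**The case against.** The mismatch in the text is hard to dispute; the case on the other side is about reach and consequence.

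- **Few patients may be affected under reading (a).** The protocol places the biopsy within Visit 3 (4.1) and stops treatment after Visit 3 (4.1.4), so post-biopsy dosing should usually be absent or short. This stands. Such dosing is still possible: the SAP writes a branch for it, and five kits with 38 tablets per bottle cover 5 × 38 = 190 days against 168 planned.
- **The longer gaps are not documented.** The SAP's 14-day window concerns biopsies taken after the last intake. Those patients fall in the branch with no subtraction, so the window gives no support to k = 14. This stands; the 7- and 14-day rows are illustrations only.
- **Understatement and 150% cannot both occur.** Correct: they are alternatives. The title and opening sentence favour active-only counting, which makes 150% plainly unintended, but the cross-reference still says otherwise.
- **Nothing inferential rests on the measure.** A reader might infer that the error biases a comparison of the doses or touches the primary result. The documents do not support that. SAP 5.3.1 plans only descriptive statistics, no test of compliance between doses is specified, and no link to the primary analysis is shown. SAP 4.4 names lack of compliance as a protocol deviation without saying which measure defines it. The all-bottle measure in the same table has three against three and serves as a cross-check.

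**Conclusion.** The definition is wrong as written for the 800 mg group, and no other section repairs it. On the natural, active-only reading the error is an understatement of k/(2D), about 0.3 points per post-biopsy day. It is confined to 800 mg patients whose last intake is after the biopsy. The effect on the group mean is smaller still, in proportion to the share of such patients, which the documents do not give. On the literal all-bottle reading every fully compliant 800 mg patient scores about 150%. The 1200 mg values are right either way.

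It would be too strong to say that compliance is understated across the 800 mg arm: patients whose last intake is on or before the biopsy have nothing subtracted. The sizes assume full adherence, D = 169 and the stated values of k. This is a minor correction to a descriptive variable.

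**What to change.** In SAP 4.5.6.1, under the numerator of the active-bottle measure:

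1. State that only lanifibranor bottles are counted, in both branches, and limit the cross-reference to the method of counting tablets per bottle.
2. When the last intake is after the biopsy, subtract 2 × (date of last intake − date of biopsy) for 800 mg and 3 × the same difference for 1200 mg, matching the existing denominators.

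The all-bottle measure above it needs no change on this point. The cost is a line or two in the SAP and the matching change in the derivation program. No data collection, dose or schedule is affected.

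In the same revision, the two bracketed notes on tablet intake in this subsection should be reconciled: one describes intake twice a day, the other each morning.

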**Lanifibranor tablets to be received up to the time of biopsy at week 24:**

The total number of lanifibranor tablets to be received is equal to:

- $((\text{Date of biopsy at week 24} - \text{Study first treatment intake date} + 1) \times 3)$  for patients receiving lanifibranor at the dose of 1200 mg
- $((\text{Date of biopsy at week 24} - \text{Study first treatment intake date} + 1) \times 2)$  for patients receiving lanifibranor at the dose of 800 mg

4.5.6.2 *Adverse Event data*

- **Treatment Emergent Adverse Event**

A Treatment Emergent Adverse Event (TEAE) corresponds to an Adverse Event (AE) that occurred on or after first dose of treatment up to 28 days post-last dose.

- **Treatment Emergent Adverse Events related to study treatment**

TEAE related to treatment is defined as a TEAE having a relationship to treatment equals to “Possibly related”, “Probably related” or with a missing relationship to study treatment.

Relationship equals to “Unlikely Related” will be considered as not related.

- **Non-Treatment Emergent Adverse Events (non-TEAEs)**

Non-TEAEs are AEs that occurred prior to treatment start.

- **Post-Treatment Adverse Events (PTAEs)**

PTAEs are AEs that occurred more than 28 days after end of treatment.

- **Serious Adverse Events**

By definition, a serious AE (SAE) is an AE that, at any time, fulfils one or more of the following criteria:

- results in death,
- is life threatening (the subject was at immediate risk of death at the time of the event; it does NOT refer to an event which hypothetically might have caused death if it were more severe),
- requires in-subject hospitalisation or prolongation of existing hospitalisation,
- results in persistent or significant disability/incapacity (substantial disruption of a person's ability to carry out normal life functions),
- is a congenital anomaly/birth defect,
- is any important medical event that may not be immediately life threatening or result in death or hospitalisation but, based upon appropriate medical judgment, may endanger the subject or may require intervention.

The seriousness of the event will be directly assessed by the investigator (specific variable within the AE database); therefore no derivation is needed.

- **Onset day**

Onset day is defined as the time between the first treatment intake date and AE onset date: (AE onset date – date of first intake + 1).

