## - Definitions:

Adverse events will be coded according to Medical Dictionary for Regulatory Affairs (MedDRA) and coded as treatment emergent (TEAE) / non-treatment emergent (non-TEAE) according to the following definitions. TEAEs are defined as events occurring on or after the day of first dose intake of study product and up to follow up visit. Additionally, events present before the first dose of study product, but worsening under treatment are considered as TEAEs. Although every effort will be made to establish the onset date and time, events with missing onset date will be considered as TEAEs. An AE that will not qualify as a TEAE will be considered as a Non-TEAE. Non-TEAES will be summarized separately from TEAES, and will be presented in the same manner as TEAES.

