#### 5.3.2 *Display of adverse events*

##### 5.3.2.1 *Overall summary of Treatment Emergent Adverse Events (TEAEs)*

The following summary statistics will be given in the safety set of patients by treatment group (Lanifibranor 800mg, lanifibranor 1200mg, lanifibranor all, placebo):

- Number (%) of patients with at least one **TEAE**
- Number (%) of patients with at least one **TEAE related to treatment**
- Number (%) of patients with at least one **TESAE**
- Number (%) of patients with at least one **TESAE related to treatment**
  
- Number (%) of patients with a **fatal TESAE**
- Number (%) of patients with a **fatal TESAE related to treatment**
  
- Number (%) of patients with at least one **mild TEAE**
- Number (%) of patients with at least one **moderate TEAE**
- Number (%) of patients with at least one **severe TEAE**
  
- Number (%) of patients with at least one **severe TEAE related to treatment**
- Number (%) of patients with at least one **severe TESAE**
- Number (%) of patients with at least one **severe TESAE related to treatment**
  
- Number (%) of patients with at least one **TEAE leading to treatment permanent discontinuation**
- Number (%) of patients with at least one **TEAE leading to treatment permanent discontinuation related to treatment**

Corresponding number of events will also be provided for each type of AEs.

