### 5.3.2.3 Analysis of Non-Treatment Emergent Adverse Events (non-TEAEs)

For Non-TEAEs, only a listing will be edited in the safety set of patients.

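### The SAP's treatment-emergent definition drops the protocol's worsening clause without declaring it, so AEs recorded with a pre-dose onset that worsen on treatment fall out of the by-arm AE tables

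*SAP*

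**What the plan says.** Protocol 9.7.2 gives two routes to treatment-emergent status. The first is timing: "events occurring on or after the day of first dose intake of study product and up to follow up visit". The second is worsening: "events present before the first dose of study product, but worsening under treatment are considered as TEAEs". Anything else is a non-TEAE, and the protocol says that non-TEAEs will be summarised separately and "will be presented in the same manner as TEAES". The same section asks for serious AEs to be listed and summarised, and for AEs leading to discontinuation to be tabulated, in both cases whatever their emergence class.

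SAP 4.5.6.2 keeps one route, an AE "that occurred on or after first dose of treatment up to 28 days post-last dose". Its complement before treatment has no exception: "Non-TEAEs are AEs that occurred prior to treatment start".

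On output, SAP 5.3.2.1 opens with "The following summary statistics will be given in the safety set of patients by treatment group", and every row that follows is a TEAE or a treatment-emergent serious AE (TESAE). The tables by system organ class and preferred term in 5.3.2.2 have the same restriction. For the remainder, SAP 5.3.2.3 says: "For Non-TEAEs, only a listing will be edited in the safety set of patients".

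SAP 4.6 sets out the modifications from the protocol's statistical section. It lists neither the change to the TEAE definition nor the narrower outputs.

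**The concern.** The worsening clause covers a patient who enters with a mild event and becomes clearly worse on study drug. Protocol 6.1.2 records AEs from consent. The screening phase can last up to 8 weeks and may include a liver biopsy, so AEs that are open at first dose are to be expected. Under the SAP rule, such an AE that turns severe or serious on treatment, or leads to stopping, is classed by when it began.

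At stake is the completeness of the by-arm AE comparison in a trial whose protocol (6.3) calls all safety variables primary. The protocol also had backstops that did not depend on emergence: a non-TEAE summary, an all-SAE summary and an all-AE discontinuation table. The SAP removes or narrows all three, so an event misclassified at the definition is not picked up in a later AE table.

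The change is also undeclared. SAP 4.6.2 goes as far as recording a small edit to the safety set, so a reader would expect a change to the TEAE definition to appear there. Protocol 9.7.4 lets SAP clarifications prevail unless they cause major inconsistencies. A programmer would therefore follow the SAP text.

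**Working it through.** The plan gives no figure on this point, so the check compares the two texts and classifies each kind of record under both.

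Inputs:

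- **Protocol 9.7.2:** TEAE by timing or by worsening; non-TEAEs summarised like TEAEs; SAE summary and discontinuation table regardless of emergence.
- **Protocol 6.1.2, 6.1.6 and 6.1.8:** AEs collected from consent and followed until resolved or stable. A symptom, syndrome or diagnosis present before first dose becomes an AE if it worsens after treatment starts. No rule says which onset date to record.
- **SAP 4.1.6.2:** a wholly missing AE start date is set to first intake, or to the AE end date if that is earlier.
- **SAP 4.5.6.2:** TEAE and non-TEAE by timing. The only derived AE timing variable runs from the onset date. There is no worsening date or flag.
- **SAP 5.1.1 and 4.1.4:** reasons for stopping treatment are described, with AE as a category and no emergence filter, by treatment group.
- **SAP 5.3.2:** by-arm AE tables for TEAEs and TESAEs only.

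| Record | Protocol 9.7.2 | SAP | By-arm AE tables under SAP |
|---|---|---|---|
| (a) Screening AE, worsens on treatment, pre-dose onset kept | TEAE | Non-TEAE | Absent; listed only |
| (b) Pre-existing condition that worsens, entered as an AE dated after first dose | TEAE | TEAE | Present |
| (c) AE with wholly missing start date | TEAE | TEAE by imputation, unless its end date precedes first intake | Present, with that exception |
| (d) As (a), and becomes serious on treatment | TEAE; also in the all-SAE summary | Non-TEAE | Absent from the TESAE tables |
| (e) As (a), and leads to stopping treatment | TEAE; also in the all-AE discontinuation table | Non-TEAE | Absent from the AE discontinuation tables; still counted in disposition (5.1.1) |

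The two documents disagree in rows (a), (d) and (e). All three depend on one condition: the record keeps its pre-dose onset date. Where that holds, the loss from SAP 5.3.2 follows directly from the text. Where the worsening is entered as an AE dated after first dose, nothing is lost.

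No other SAP section restores the worsening route.

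**The case against.** The best counter-argument is protocol 6.1.8. If a pre-existing problem that worsens is entered as an AE dated at the worsening, it meets the SAP's timing rule and stays in the tables. This stands, and it limits the point. A reader might infer that a screening AE always keeps its pre-dose date when it worsens; neither document says so, and the eCRF was not supplied. But 6.1.8 sets no onset date and does not tell the site to open a second record for something already recorded as an AE. The protocol also carries the worsening clause in 9.7.2 alongside 6.1.8, so it did not rely on 6.1.8 alone.

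A second temptation is to say that these events leave every by-arm table. They do not. The disposition table still counts AE discontinuations, and the laboratory, vital-sign and ECG summaries do not depend on TEAE status. The events also stay in the non-TEAE listing. SAEs are reported within 24 hours, and the DSMB receives a listing of all AEs and SAEs. The loss concerns the by-arm AE tables of SAP 5.3.2.

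A third is that the drug-placebo contrast must be understated. The rule is the same in every arm. Counts can fall, but the contrast shrinks only if worsening is more frequent on drug, and the documents do not show that.

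**Conclusion.** The SAP departs from protocol 9.7.2 without declaring it, and following the SAP text misclassifies AEs that are recorded with a pre-dose onset and worsen on treatment. They become non-TEAEs, are only listed, and are missing from the by-arm TEAE, severity, relatedness, serious and discontinuation tables in SAP 5.3.2.

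The conclusion rests on two conditions:

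- The worsening is not separately entered as an AE dated after first dose.
- The clause is still in the protocol version that governs the analysis. SAP section 2 cites version 5.1, and the protocol supplied is version 5.0. Nothing seen suggests that the clause was removed, but the sponsor should confirm it.

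The size cannot be given. Neither document reports how often screening AEs occur or worsen, and a per-arm count would only be an assumed rate multiplied by the arm size. A patient would also leave the row for at least one TEAE only if they had no other TEAE. This should be corrected because the rule contradicts the protocol and is cheap to repair; a large effect has not been shown.

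**What to change.** 1. In SAP 4.5.6.2, restore the protocol's second route, so that an event already present before first dose that worsens under treatment is a TEAE, and amend the non-TEAE definition to match. Alternatively, state that a worsening is entered as a new AE whose onset is the date of worsening, and confirm that the data were collected that way.
2. Reconcile SAP 5.3.2 with protocol 9.7.2: the non-TEAE summary, the summary of all SAEs, and the table of all AEs leading to discontinuation, the last two regardless of emergence.
3. Declare in SAP 4.6 any departure that is intended.
4. Confirm that protocol version 5.1 kept the clause.

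The definition costs a sentence and a derivation flag, and the reconciled outputs a few additional tables. The flag assumes that the database shows when an AE worsened, which the documents do not establish. If it does not, the AEs open at first dose need a blinded review before database lock.

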#### 4.1.3 *Follow-up Period*

Safety of withdrawal from treatment groups is assessed during a 30-day assessment phase.

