### - **Treatment Emergent Adverse Events**

A given TEAE will be counted once only per patient. The percentages will be calculated in relation to the population exposed (i.e., safety population). All TEAEs will be analyzed, irrespective of their causal relationship with lanifibranor. Recapitulative tables will be provided, showing the following:

- count of exposed patients,
- count and percentage of patients with at least one TEAE,
- count and percentage of each TEAE: TEAEs will be sorted by decreasing order of organ system frequency then by decreasing order of preferred term frequency,
- count and percentage of each TEAE, not taking into account organ system.

In addition, TEAEs will be described according to their time to onset with same categories as for duration of exposure, their maximal intensity and their relationship to lanifibranor, gender and age of patient, time from first intake, outcome, seriousness criteria, corrective treatment, duration, treatment received and action taken. Patient data listings will be provided for all AEs, TEAEs, AEs leading to study discontinuations and SAEs.

Deaths and Serious Adverse Events Incidence of SAEs (irrespective of their emergence classification and relationship to lanifibranor) and deaths will be listed and summarized.

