###### Safety (Treatment Emergent Adverse Event):

- Adverse events that started after 28 days will be considered as Post Treatment Adverse Events (PTAE)

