#### 5.1.1 Patients disposition

The number (%) of patients included in each population will be described overall and then by country: screened patients, non-randomised patients, randomised patients, FAS, EPP, safety patients and PP patients. Percentages will be calculated over the number of randomised patients.

First Patient First Visit, Last Patient First Visit and Last Patient Last Visit will also be described overall and then by country. "First Visit" will be defined as the screening visit (V-1).

The reasons for non-randomisation will also be described among the non-randomised patients, consisting of screening failed patients.

In addition, in order to have an overview of patients' disposition, the following elements will be described by treatment group and overall in the FAS for each post-randomisation visit:

- Number (%) of patients who performed the visit (Yes/No)
  - o If Yes, Number (%) of patients still under treatment (Yes/No)
  - o If No:
    - Number (%) of patients still ongoing (Yes/No)
    - Number (%) of patients still under treatment (Yes/No)

Due to the CRF design, Visit 3 was either completed per protocol and performed at week 24, or performed as part of early termination visit. For analysis, visit 3 will be splitted in 2:

- Visit 3 performed as part of early termination visit (i.e. premature EOT)
- Visit 3 performed as part of week 24 visit.

Same strategy will be applied for visit 4:

- Visit 4 performed after a visit 3 performed as part of early termination visit (i.e. follow-up visit following premature EOT)
- Visit 4 performed at week 28 after a visit 3 performed as part of week 24 (i.e. follow-up visit following treatment completed until week 24).

Additionally, for visit 4 performed after a visit 3 as part of week 24, it will be detailed whether visit 4 has been performed within 4 weeks +/- 2 weeks after visit 3 or not.

In order to have an overview of biopsies' disposition, the following elements will be described at Visit 3 by treatment group and overall in the FAS

- Number (%) of biopsies available (Yes/No)

- If Yes, Number (%) of biopsies still under treatment (Yes/No), i.e. within maximum 14 days after last intake
- If No, Number (%) of biopsies non-available (non-readable, patient refusal, premature permanent treatment discontinuation)

Additionally, patients' treatment status (Treatment completed, Treatment prematurely withdrawn) at time of study end will be described in the FAS overall and by treatment group.

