### 5.3.2.4 Analysis of Post-Treatment Adverse Events (PTAEs)

For PTEAEs, only a listing will be edited in the safety set of patients.

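### The SAP ends the treatment-emergent window at day 28 and tabulates only treatment-emergent SAEs and deaths, where the protocol runs to the follow-up visit and summarises all of them; the change is undeclared

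*SAP*

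**What the plan says.** **Protocol (version 5.0), section 9.7.2.** TEAEs are "events occurring on or after the day of first dose intake of study product and up to follow up visit". Any AE that is not a TEAE is a non-TEAE, and non-TEAEs are to be summarised separately but presented in the same way as TEAEs. For serious events the instruction is: "Incidence of SAEs (irrespective of their emergence classification and relationship to lanifibranor) and deaths will be listed and summarized".

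**SAP.** Section 4.5.6.2 counts an AE as treatment-emergent if it "occurred on or after first dose of treatment up to 28 days post-last dose". It adds a class that the protocol does not have: "PTAEs are AEs that occurred more than 28 days after end of treatment". Section 4.1.6.3 repeats the day-28 rule and makes clear that an event is classified by when it started. For PTAEs, section 5.3.2.4 says that "only a listing will be edited in the safety set of patients"; section 5.3.2.3 says the same for pre-treatment events. The by-arm tables in 5.3.2.1 and 5.3.2.2 are confined to TEAEs, treatment-emergent SAEs and fatal treatment-emergent SAEs.

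**Timing of V4.** Protocol 4.1 and 5.3.6 place V4 four weeks after V3 or the end of treatment, and the synopsis gives a window of ±3 days referred to V0. Protocol 4.1.3 describes the purpose and length slightly differently: "Safety of withdrawal from treatment groups is assessed during a 30-day assessment phase".

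**Declared changes.** SAP 4.6 lists departures from the protocol's statistical section, including a revised safety-set definition in 4.6.2. It mentions neither the TEAE window nor the SAE and death summary.

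**The concern.** Two things differ between the documents, and neither is announced.

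First, the SAP cut-off falls on the nominal day of the only planned off-treatment visit. V4 includes a physical examination and safety laboratory tests, and protocol 9.7.3 turns new clinically significant findings into AEs. An abnormality first detected and dated at V4 is a TEAE if the visit is on day 27 and a PTAE if it is on day 30. The protocol would count both.

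Second, whatever the visit timing, the protocol's summary of SAEs irrespective of emergence, and of deaths, has no counterpart in the text of SAP 5.3.2. An SAE or death with onset after day 28 would be found in a listing but in no by-arm table that the SAP text describes. The same holds for an SAE between consent and first dose.

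Safety is part of the study objective, and protocol 6.3 calls all safety variables primary. With 247 patients randomised 1:1:1, an arm has about 247/3 ≈ 82 patients, so a single SAE moves an arm's incidence by about 1/82 ≈ 1.2 percentage points. Small shifts in what is counted can therefore be visible.

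**Working it through.** The documents give no figure for how many V4 visits fall after day 28, so there is none to reproduce.

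**Step 1: the two rules side by side**

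| Item | Protocol 9.7.2 | SAP 4.5.6.2, 5.3.2 |
|---|---|---|
| End of TEAE window | Follow-up visit (V4) | Day 28 after last dose |
| AEs that are not TEAEs | Summarised like TEAEs | Listed only |
| SAEs | Listed and summarised, any emergence | By-arm tables for treatment-emergent SAEs only |
| Deaths | Listed and summarised | By-arm tables for fatal treatment-emergent SAEs only |

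The last three rows need no arithmetic.

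**Step 2: inputs for the window**
- Nominal V3 to V4 gap: (28 − 24) weeks × 7 = 28 days (protocol schedule tables), equal to the SAP cut-off.
- Visit window: ±3 days referred to V0 (protocol synopsis).
- Last dose: treatment stops after V3 (protocol 4.1.4), and on trough-sampling days the dose follows the sample (protocol 7.1.1). The last dose can thus be on the V3 day (lag 0) or the day before (lag 1).
- Assumption, not in the documents: the V3 and V4 offsets a and b are independent and uniform on −3, …, +3, giving 7 × 7 = 49 equally likely pairs.

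**Step 3: share of V4 visits after day 28**

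Days from last dose to V4 = 28 + b − a + lag.
- Lag 0: past day 28 when b > a, which is 21 of 49 pairs = 42.9%.
- Lag 1: past day 28 when b ≥ a, which is 28 of 49 pairs = 57.1%.
- Lag 0, the other side: V4 is before day 28 when b < a, again 21 of 49 = 42.9%. In the other 7 of 49 it is on day 28.

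**Step 4: onset time lost**

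Only onsets from day 29 to V4 change class, so the loss per patient is max(0, b − a + lag) days.
- Lag 0: a difference of d days occurs in 7 − d pairs. The sum of d(7 − d) for d = 1 to 6 is 6 + 10 + 12 + 12 + 10 + 6 = 56. The mean is 56/49 = 1.1 days and the maximum 6. As a share of the follow-up after the last dose this is 56/(49 × 28) = 4.1%. As a share of the whole 168 + 28 = 196 days it is 1.14/196 = 0.6%.
- Lag 1: the sum is 84, so the mean is 84/49 = 1.7 days and the maximum 7.

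**Step 5: sensitivity to the assumed spread**
- V4 uniform over ±14 days around its nominal date 28 days after V3, lag 0: 14/29 = 48.3% after day 28; mean loss 105/29 = 3.6 days, maximum 14.
- Follow-up of 30 days, as in protocol 4.1.3, with ±3-day windows: 34/49 = 69.4% (lag 0) to 39/49 = 79.6% (lag 1).
- Every visit exactly on schedule: 0% at lag 0, 100% at lag 1 (V4 on day 29).

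**The case against.** A fair defence has several parts.

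- **Day 28 is a natural reading of the follow-up visit.** V4 is due four weeks after V3, and protocol 6.1.6 uses 28 days after treatment for documenting the outcome of unrelated ongoing AEs. Protocol 9.7.4 lets SAP clarifications prevail unless they cause major inconsistencies. A fixed day also does not vary with attendance, and it gives an end to patients without a V4, for whom the protocol rule gives none. This stands as a reason why day 28 could be chosen. It does not stand for the SAE and death summary, because leaving out a required summary is a removal and not a clarification.
- **The difference runs both ways.** Where V4 is before day 28, the SAP window is the longer one. That is true, although after the last visit protocol 6.2.2 asks only for SAEs thought to be caused by the product or a protocol procedure, so little would be gained there.
- **A reader might infer that whatever is found at about half of the V4 visits leaves the by-arm tables.** The documents do not support this. Classification is by onset, so an event reported at a late V4 that began by day 28 stays a TEAE. The 43% to 57% is a share of visits, not of events. V4 laboratory values are still described by arm (SAP 5.3.3.3, with the Week 28 rule for completers in 4.1.6.3), as are weight and blood pressure to week 28 (5.3.3.4).
- **A reader might also infer that onsets up to day 42 are routinely cut, because SAP 5.1.1 says that** "it will be detailed whether visit 4 has been performed within 4 weeks +/- 2 weeks after visit 3 or not". That sentence concerns disposition, and the matching note in 4.1.6.3 concerns which Week 28 data are described. The protocol's visit window remains ±3 days.
- **Sources.** The SAP is written to protocol 5.1 and refers to separate table shells. Neither was available, so an unchanged 9.7.2 and the absence of the table from the shells cannot be confirmed. This stands and limits the conclusion to the texts at hand.

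**Conclusion.** The point holds in two parts of unequal weight.

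The firmer part is that the SAP text provides no by-arm summary of SAEs irrespective of emergence, or of all deaths, and only lists the AEs that protocol 9.7.2 wants presented like TEAEs. This rests on no assumption about visit dates. It is also undeclared in SAP 4.6, where another safety change is declared.

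The lesser part is the window. Assuming uniform ±3-day spreads, about 43% (last dose on the V3 day) to 57% (the day before) of V4 visits can fall after day 28. The onset time moved out of the by-arm tables is small: a mean of about 1.1 days per patient and at most 6 when the last dose is on the V3 day. Most of its practical effect would be on abnormalities first detected and dated at V4. After early discontinuation the gap from last dose to V4 may be longer; the documents do not allow that to be sized.

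Later events remain in listings, and efficacy is untouched. It would go too far to say that the safety comparison is distorted, or that late SAEs are hidden. What is shown is that required summaries are absent from the SAP text and that the two windows disagree, subject to protocol 5.1 and the table shells.

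**What to change.** 1. **SAP 5.3.2:** add one by-arm table of all SAEs and all deaths irrespective of emergence, as protocol 9.7.2 requires.
2. **SAP 4.5.6.2 and 4.1.6.3:** reconcile the TEAE window with the protocol in one of two ways.
   - Count onsets up to V4, using day 28 after the last dose as the end when V4 is missing or earlier. State that the day-28 provision extends the protocol rule, which ends at V4 and is silent on a missing V4.
   - Or keep day 28, declare the change with its reason in SAP 4.6, and summarise PTAEs by arm instead of only listing them.
3. **Check first** whether protocol 5.1 changed section 9.7.2 and whether the table shells already hold the SAE and death table. If they do, the SAP text only needs to say so.

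The cost is SAP wording, one derived flag and one or two extra tables from data already collected. Reported counts may rise slightly.
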